10.7 Pathologic Complete Response

No evidence of viable tumor cells on complete pathological evaluation of the surgical specimen per institutional standard of care.

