To assess the hypothesis that higher mutational load is associated with pCR rate, the study will assess the association between overall mutational load and pCR rate. We will first calculate the per megabase mutation rate for each individual. Then we will use logistic regression to regress pCR status on the mutation rates and use a 1-degree freedom likelihood ratio test to obtain a p-value for the association between response and mutation rate. We will control the type I error at the two-sided alpha=0.05 level. We estimated the minimal detectable odds-ratio under the assumption that we will collect exome sequencing data on 25 patients and that we will control the type I error rate at the two-sided alpha=0.05 level. In prior data, the median number of mutations per megabase in desmoplastic melanoma was found to be 62 and the 25th and 75th percentiles were 33 and 101, respectively (private communication, [name] to [name], 11/18/2014). Therefore, by matching the quantiles, we approximate the distribution of the per megabase mutation rate across patients as a Weibull with shape parameter 1.4 and scale parameter 80. Assuming a baseline response rate of 5%, we anticipate over 80% power to detect a log odds-ratio of 0.31 (corresponding to an odds-ratio of 1.36) for each 10 mutation increase in the per megabase mutation rate. If logistic regression is unstable or behaves poorly, e.g. due to low response rates, we will also consider robust and flexible alternatives such as the Wilcoxon test to compare mutation rates between responders and nonresponders.

The study will examine whether change in T-cell infiltration following treatment is higher in the DM patients who respond. Specifically, we will compute the change in CD8 expression from baseline to resection and then compare the change between responders and non-responders using a two-sample t-test. We will control type I error at the alpha=0.05 level. Assuming that 25% of patients respond, then we anticipate 80% power to detect a difference in mean CD8 expression change 1.35 standard deviations. We will repeat the analysis comparing the change in CD8 expression from baseline to week 4 to determine whether T-cell infiltration in the on-treatment biopsy is associated with response at resection.

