The study will examine adaptive immune resistance by first evaluating whether PD-L1 expression is increased at Week 4 and resection as compared to baseline using paired t-tests and controlling the type I error at the two-sided alpha=0.05 level. With 25 patients, we anticipate 80% power at each time point to detect a mean difference in expression of 0.58 standard deviations. We will further evaluate whether increased PD-L1 expression at Week 4 or at resection is associated with response. Specifically, we will compute the change in expression from baseline to resection and then compare the change between responders and non-responders using a two-sample t-test. We will control type I error at the two-sided alpha=0.05 level. Assuming that 25% of patients respond then at each time point we anticipate 80% power to detect a difference in mean PD-L1 expression change of 1.35 standard deviations. We will repeat the analysis comparing the change in PD-L1 expression from baseline to week 4 to determine whether T-cell infiltration in the on-treatment biopsy is associated with response at resection. In addition to our assessment of overall mutational load, we will further conduct a neoantigen analysis. Specifically, we will predict the immunogenicity of each nonsynonymous somatic mutation using NetMHC. We will then use logistic regression to regress pCR status on the number of predicted immunogenic mutations, computing a pvalue using a 1-df test and controlling type I error at the two-sided alpha=0.05 level.

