11.2 Cohort B

a. As a pilot study, Cohort B will use a single stage design with an accrual goal of 21 eligible patients. The anticipated accrual rate for Cohort B is 1 patient per month. Assuming an ineligibility rate of 20%, the study will accrue 26 total patients to enroll 21 eligible patients.

b. Primary Endpoint

The primary endpoint for Cohort B is complete response rate (CR). Given that Cohort B is intended as a pilot trial, we propose single stage design with the assumption that a true CR of 20% or higher indicates that the treatment is of considerable interest for patients with unresectable/metastatic DM whereas a true CR of 5% or lower indicates that the treatment will not be of further interest. Specifically, we will enroll 21 eligible patients with unresectable/metastatic DM. Three or more complete responses out of 21 would be considered evidence that the treatment warrants further study, provided other factors such as toxicity and overall survival also appear favorable. This design has an alpha of 8.5% (i.e. probability of declaring the regimen warrants further study when the true CR is 5%) and a power of 82% (probability of declaring the regimen warrants further study when the true CR is 20%). The higher alpha and lower power used in this design reflect the intention to use this as a pilot trial.

Secondary Endpoints

For the secondary endpoints, 21 eligible patients will be sufficient to estimate the PFS and OS at a particular time point (e.g. 9 weeks) to within ±21.4% (95% confidence interval). However, since PFS is estimated only among patients who do not undergo resection, we will only be able to estimate the PFS to within ±21.9%, ±22.5%, or ±23.9% (95% confidence intervals) if the percentage of patients who undergo resection is 5%, 10%, or 20%, respectively.

d. Translational Medicine Objectives: The statistical analysis of the translational medicine objectives for Cohort B will be the same as for Cohort A except we will use CR as the endpoint instead of pCR.

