15.0 SPECIAL INSTRUCTIONS

15.1 Specimen Submission for Translational Medicine

Specimens for Translational Medicine studies outlined in Section 18.1 are required for participation in this study.

- a. Specimens must be submitted at the timepoints listed below. Collection instructions are outlined in Section 15.1c and submission instructions are outlined in Section 15.1e. NOTE: With patient consent, leftover specimens will be banked for future unknown use.
- b. Specimens must be submitted at the following times (see Section 9.0):
 - 1. Three cores (at least 18 gauge needle) to be obtained from primary (preferred) or metastatic lesions (avoid lymph node biopsy if possible) and made into three different FFPE blocks (one core per block). Sending all three blocks is preferred. Thirty slides (minimum bum thick) per block from each of the blocks may be submitted if the institution cannot release pathology paraffin embedded blocks, at the following times:
 - Baseline (required) prior to the start of study treatment. Initial/Archival biopsy may be used if 4 cm x 30 slides can be provided). Submit tissue within 30 days after registration.
 - Biopsy between 3 and 5 weeks after initiation of treatment (required for all patients with residual disease to biopsy). Submit tissue within 30 days of collection.
 - Surgical specimen from each site of surgical resection (required if surgical resection is performed). Submit tissue within 30 days of collection.
 - Progression/relapse (optional). Submit tissue within 30 days of collection.

[figure not shown]
Submit formalin fixed paraffin embedded (FFPE) tissue according to guidelines below.

- 2. Twenty mL whole blood in vacutainer tubes with EDTA coating. Collect at the following times:
 - Baseline (mandatory prior to the start of study treatment)

Specimen Collection Instructions

- Standard collection of Paraffin Embedded Tissue Block.
 - Place the fresh tissue in formalin. Do Not Exceed 24 hours fixation time.
 - Fixed tissue must be paraffin embedded within 24 hours.
 - Send H & E (Hematoxylin and Eosin) stained section if it is routine practice for the site. Otherwise, sending the block without the H&E slide is adequate.

- 2. Standard collection of Slides.
 - Slides may be processed according to local pathology guidelines.
- 3. Standard Instructions for Shipping Paraffin Embedded Tissues and Slides:
 - Include in shipment:
 - i. Tissue as outlined above

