Quantitative analysis of T cell infiltration and circulating tumor DNA (ctDNA) profile: To analyze whether baseline CD8+ cell infiltration and ctDNA profile are correlated with response to anti-PD1 therapy, and whether PD-1 blockade can increase CD8+ cell infiltration in DM patients, slides taken from standard formalin-fixed paraffin-embedded (FFPE) tissue blocks obtained from baseline, 4 week (on treatment), and 9 week biopsies will be stained by quantitative multiplexed immunohistochemistry (IHC) for, at the minimum, S100 and CD8 to determine the presence of CD8+ T cells inside tumors and in the invasive margin. ctDNA profiling will be performed on plasma processed from patient baseline blood sample to determine the amount or fraction of ctDNA corresponding to the genetic profile of the patient tumor biopsies. Slides will be analyzed using quantitative digital pathology following published methods, such as described by Tumeh et al. and Angelo et al.. (1, 2) This analysis will provide a predictive score for response or lack of response to pembrolizumab based on the baseline CD8+ T cell infiltration or ctDNA profile.

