Method: Slides will be stained with, at the minimum, S100 and CD8 (one slide per stain, or multiple stain per slide as appropriate for chosen quantitative multiplexed IHC technique) at a core facility with the instrumentation, such as the UCLA Anatomic Pathology IHC Laboratory (CLIA approved lab). Immunostaining will be performed using staining procedures appropriate for the specific quantitative multiplexed IHC technique and validated by the Translational Medicine team, for example, Leica Bond III autostainers using Leica Bond ancillary reagents and REFINE polymer DAB detection system (Leica DS9800). Antibodies used will include rabbit polyclonal S100 (DAKO, 1/1,000 dilution, low pH retrieval), mouse anti-CD8 clone C8/144B (DAKO, 1/100, low PH retrieval), and all staining will be performed on Dako autostainers, and visualized with DAB. Slides will be baked for 60 minutes at 60°C. Procedure involves dewaxing, heat-retrieved in Bond ER1(pH6) buffer for 20 minutes, and sequential incubations with primary antibody, postprimary reagent, and polymer for 15 minutes, 8 minutes, and 8 minutes, respectively, and subsequent DAB chromogen application and Hematoxylin counterstaining. All stained slides will be evaluated in a blinded fashion by one dermatopathologist and one investigator trained to identify the features of melanoma, and the presence of CD8 within the tumor parenchyma (tumor) and the connective tissue surrounding the tumor (invasive margin) will be examined.

All slides will be scanned at an absolute magnification of X200 (resolution of 0.5 mm/pixel). An algorithm was designed based on pattern recognition that quantified immune cells within S100-positive areas (tumor) and S100-negative areas (invasive margin). Image analysis based on RGB (red, green, blue) spectra will be used to detect all cells by counterstaining with haemotoxylin (blue), and DAB or fast red. The algorithm calculated the density (cells mm⁻²) and percentage cellularity (% positive cells/all nucleated cells) using Indica Labs Halo platform.

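### Cohort A compares CD8 and PD-L1 change to resection by pCR status, but reads both in the specimen whose lack of viable tumor defines pCR; the baseline CD8 analysis promised in Section 18.1 is missing

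*Combined protocol and SAP*

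**What the plan says.** **Who is a responder.** Section 10.7 defines pCR as "No evidence of viable tumor cells on complete pathological evaluation of the surgical specimen". Section 11.2d confirms that the Cohort A translational tests use this endpoint: Cohort B follows the same analyses "except we will use CR as the endpoint instead of pCR". Under Section 11.1b, patients who have no surgery on protocol, for any reason, count as non-responders.

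**What is compared.** For CD8, Section 11.1d will "compute the change in CD8 expression from baseline to resection and then compare the change between responders and non-responders" by a two-sample t-test. TCR clonality and PD-L1 get the same comparison. Each is assigned 80% power for 1.35 SD, assuming 25% of patients respond, and each is repeated for the change from baseline to Week 4. A paired test of PD-L1 over time comes with this statement: "With 25 patients, we anticipate 80% power at each time point to detect a mean difference in expression of 0.58 standard deviations".

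**How the biomarkers are read.** The CD8 algorithm in Section 18.1 "quantified immune cells within S100-positive areas (tumor) and S100-negative areas (invasive margin", and PD-L1 follows the same digital pathology method. TCR clonality is calculated from T-cell receptor sequences in DNA extracted from the tissue block.

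**What tissue exists.** Section 15.1b requires baseline tissue from everyone and a surgical specimen whenever resection is done. The on-treatment biopsy is "required for all patients with residual disease to biopsy".

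**What Section 18.1 promises at baseline.** One stated purpose is "To analyze whether baseline CD8+ cell infiltration and ctDNA profile are correlated with response to anti-PD1 therapy", leading to a predictive score.

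**The concern.** The grouping variable and the measurement come from the same piece of tissue. A patient is a responder because the resection specimen holds no viable tumor, and the plan then asks how CD8 and PD-L1 in that specimen differ from those in patients whose specimens do hold tumor. Both scoring compartments are defined by reference to tumor: the tumor itself and the tissue bordering it. The plan does not say which compartment supplies the analysis variable, or how to score a specimen with no viable tumor.

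Followed literally, the plan leads to one of two results. Either responders have no intratumoral value, or a value from regressed tumor bed is entered for them and compared with live tumor. The second can produce an association that largely restates the endpoint definition.

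The baseline comparison avoids this problem, because baseline tissue is required of all patients and precedes the outcome. Section 18.1 describes that analysis for CD8, and the Section 2.0 background rests on pre-treatment CD8 at the invasive margin as a predictor. Section 11.1d nevertheless contains no baseline CD8 test against response. Among the biomarkers in question, only ctDNA has one.

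**Working it through.** **Inputs.** N = 25 eligible patients (Section 11.1a). Response share 25%, 80% power and 0.05 significance level (Section 11.1d). The level is stated as two-sided for clonality and PD-L1; the side is not stated for CD8.

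**Step 1: reproduce 1.35 SD.** Expected responders are 0.25 × 25 = 6.25, leaving 18.75 non-responders. For a two-sample t-test, df = n1 + n2 − 2 and the noncentrality is d / √(1/n1 + 1/n2).
- √(1/6.25 + 1/18.75) = √(0.1600 + 0.0533) = 0.462, so the noncentrality at d = 1.35 is 2.92. Two-sided power is 79.9%, and the difference detectable with 80% power is 1.351 SD.
- In whole patients, 6 vs 19 gives 1.370 SD, with 78.8% power at 1.35 SD.
- A one-sided test at 6.25 vs 18.75 would give 1.18 SD, so the CD8 figure was evidently also two-sided.

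The stated figure is arithmetically right. It needs a usable change value from all 25 patients, including every expected pCR patient.

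**Step 2: reproduce 0.58 SD.** For a paired t-test, df = n − 1 and the noncentrality is d√n. With n = 25, the detectable difference is 0.584 SD, and power at 0.58 SD is 79.5%. This reproduces too, again only with all 25 measured.

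**Step 3: who can lack a resection value.**
- pCR patients supply a specimen, but it has no viable tumor in which to score intratumoral CD8 or PD-L1.
- Non-responders without surgery have no resection specimen. The Section 9.1 footnote on surgery asks for a biopsy if disease is unresectable at 9 weeks, so some may have week 9 tissue, but that is not a resection.

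The plan gives no number for either group, so the following are assumptions shown as a range.

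| Two-sample: responders vs non-responders | Detectable difference, 80% power | Power at 1.35 SD |
|---|---|---|
| 6 vs 19 | 1.37 SD | 79% |
| 5 vs 19 | 1.47 SD | 73% |
| 4 vs 19 | 1.62 SD | 65% |
| 3 vs 19 | 1.83 SD | 54% |
| 2 vs 19 | 2.20 SD | 41% |
| 6 vs 15 | 1.43 SD | 75% |
| 3 vs 15 | 1.89 SD | 52% |

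If only intratumoral values are used and no pCR specimen has one, the split is 0 vs 19 and the test cannot be run. For the paired PD-L1 test, 19 evaluable pairs give 0.68 SD, with 67% power at 0.58 SD.

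**Step 4: Week 4.** The same table applies. That biopsy is required only where residual disease remains, so the missing values may fall among the best responders. Week 4 lessens the problem but does not remove it.

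**Step 5: baseline.** Baseline tissue is required of all patients. If all 25 have a usable CD8 reading, the 1.35 SD figure carries over to a baseline comparison without change.

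**The case against.** The strongest reply is that the responder group can be measured. pCR patients supply a required surgical specimen. Section 11.1d does not restrict CD8 expression to the intratumoral compartment. Section 18.1 reports density per area and percentage of all nucleated cells, and either can be computed in tissue without tumor cells. PD-L1 is not confined to tumor cells. TCR clonality needs T cells only. Each comparison is also repeated at Week 4.

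Much of this stands, and it rules out several stronger readings that a reader might infer:
- *That responders cannot be measured at resection at all.* The documents do not support this. Stromal and tumor-bed cells can be counted. What is undefined is the intratumoral value.
- *That TCR clonality fails in the same way.* It does not. The difficulty there is one of interpretation, tumor bed against tumor.
- *That Section 18.1 promises a baseline comparison with response for all three biomarkers.* It does so for CD8 and ctDNA only. Its PD-L1 question is about induction, which is a change.
- *That objectives 1.3b, 1.3c and 1.3d all become unanswerable.* Objective 1.3d names no correlation with response, 1.3b also covers ctDNA, for which a baseline test is planned, and Week 4 remains.
- *That 0.68 SD is the correct paired figure.* It is one scenario. Non-responders without surgery could lower the number further, and immune-cell PD-L1 in the tumor bed could raise it.

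The reply does not supply a scoring rule for specimens without viable tumor. Nor does it make a tumor-bed reading comparable with a live-tumor reading when the grouping is the presence of tumor.

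**Conclusion.** The point holds for CD8 and PD-L1 at resection in Cohort A. The intratumoral value is undefined in pCR specimens, and any substitute from the tumor bed is confounded with the endpoint. For TCR clonality it holds only as a limit on interpretation. The omission of the baseline CD8 comparison is a plain mismatch between Sections 18.1 and 11.1d.

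The size depends on how many patients have usable pairs, which the plan does not state. With 5 scorable responders against 19 non-responders the detectable difference is 1.47 SD, and with 3 it is 1.83 SD, against the stated 1.35 SD. The paired PD-L1 figure becomes 0.68 SD if 19 are evaluable, against 0.58 SD. The scenarios assume a 25% pCR rate and a two-sided 0.05 level; those quoted here keep 19 non-responders in the two-sample test.

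These are other objectives. The primary test, 4 or more pCRs among 25 patients, is untouched: its exact error rate is 3.4% and its power is 90.4%, as Section 11.1b states after rounding. The change is worth making but is not critical.

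**What to change.** Revise Section 11.1d as follows.

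1. Add baseline CD8, in tumor and in invasive margin, pCR versus non-pCR, as a planned comparison, and attach the 1.35 SD figure to it. Baseline clonality and PD-L1 may be added as exploratory.
2. Make the change from baseline to Week 4 the main change comparison for CD8 and PD-L1. Report how many responders had no residual lesion to biopsy.
3. Do not test intratumoral CD8 or PD-L1 change to resection by pCR status. Describe resection values by compartment: tumor bed for pCR specimens, tumor and margin for the rest. Keep TCR clonality at resection as descriptive, or test it with the tumor-bed caveat stated.
4. Give detectable differences on evaluable pairs as scenarios, for example paired PD-L1 0.68 SD at 19 pairs, and two-sample 1.47 SD at 5 vs 19 or 1.83 SD at 3 vs 19.

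The cost is wording, with no new patient, specimen or assay. The stated figures become less favorable, and the baseline CD8 comparison adds to the tests run at the 0.05 level.

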To assess the hypothesis that ctDNA fraction at baseline and week 4 are associated with response in DM patients, we will assess the association between response and ctDNA fraction using a two-sample t-test at the two-sided α =0.05 level. Assuming that 25% of patients respond, then we anticipate 80% power to detect a difference in mean ctDNA fraction of 1.35 standard deviations.

To assess the hypothesis that TCR clonality is higher in DM patients who respond, suggesting that the T-cells are targeting the tumor, we will compute the clonality metric as the normalized Shannon entropy for all patients at baseline, Week 4, and resection. We will then compute the change in clonality metric from baseline to resection. The change in clonality will be compared between responders and non-responders using a two-sample t-test with significance determined at the two-sided alpha=0.05 level. Assuming that 25% of patients respond, then we anticipate 80% power to detect a difference in clonality change of 1.35 standard deviations. We will repeat the analysis comparing the change in clonality from baseline to week 4 to determine whether T-cell clonality in the on-treatment biopsy is associated with response at resection.

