To assess the hypothesis that ctDNA fraction at baseline and week 4 are associated with response in DM patients, we will assess the association between response and ctDNA fraction using a two-sample t-test at the two-sided $\alpha = 0.05$ level. Assuming that 20% of patients respond, then we anticipate 80% power to detect a difference in mean ctDNA fraction of 1.61 standard deviations.

To assess the hypothesis that TCR clonality is higher in DM patients who respond, suggesting that the T-cells are targeting the tumor, we will compute the clonality metric as the normalized Shannon entropy for all patients at baseline, Week 4, and progression. We will then compute the change in clonality metric from baseline to progression. The change in clonality will be compared between responders and non-responders using a two-sample t-test with significance determined at the two-sided alpha=0.05 level. Assuming that 20% of patients respond, then we anticipate 80% power to detect a difference in clonality change of 1.61 standard deviations. We will repeat the analysis comparing the change in clonality from baseline to Week 4 to determine whether T-cell clonality in the on-treatment biopsy is associated with response at progression.

The study will examine adaptive immune resistance by first evaluating whether PD-L1 expression is increased at Week 4 and progression as compared to baseline using paired t-tests and controlling the type I error at the two-sided alpha=0.05 level. With 21 patients, we anticipate 80% power at each time point to detect a mean difference in expression of 0.64 standard deviations. We will further evaluate whether increased PD-L1 expression at Week 4 or at progression is

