Analysis of TCR clonality in tumors: To answer the question whether the T cell response is targeting specific tumor antigen (mono-clonal) or a non-specific process (poly-clonal) in the tumors, we will analyze TCR clonality by deep sequencing the TCR V β CDR region using the ImmunoSeq assay from Adaptive Biotech as described. (3) From thick slides of FFPE tissues taken at baseline, 4 weeks, and 9 weeks, we will isolate DNA and submit it for TCR V β sequencing. This analysis will provide information about the clonality or diversity of T cells infiltrating tumors in DM samples. DNA analysis will be performed by the UCLA Immunogenetics core laboratory (CLIA approved lab).

DNA will be isolated from FFPE thick cuts followed by extraction using a DNeasy kit (Qiagen). Melanin will be removed from visibly pigmented melanoma samples using a PCR Inhibitor Removal kit (ZymoResearch). TCR V β CDR3 regions will be amplified and sequenced using the survey ImmunoSeq assay in a multiplexed PCR method using 45 forward primers specific to TCR V β gene segments and 13 reverse primers specific to TCR V β gene segments (Adaptive Biotechnologies). Reads of length 87bp will be obtained using the Illumina HiSeq System. For each sample, Shannon entropy will be calculated on the clonal abundance of all productive TCR sequences in the data set. Shannon entropy will be normalized to the range by dividing Shannon entropy by the logarithm of the number of unique productive TCR sequences in the data set. This normalized entropy value will be then inverted (12 normalized entropy) to produce our clonality metric.

Analysis of adaptive immune resistance mechanism in tumors: Slides taken from standard FFPE tissue blocks obtained from baseline, the on treatment biopsy (week 4) and the week 9 biopsy/resection will be stained by quantitative multiplexed immunohistochemistry (IHC) for a set of multiple immune-relevant biomarkers, including PD-L1 (SP142, Spring Bioscience), to evaluate whether PD-L1 can be induced by PD-1 blockade, the patient's immune response, and which is correlated with response. Slides will be analyzed using quantitative digital pathology following the methods described for Quantitative analysis of T cell infiltration. Analysis will be performed at core facilities with the relevant instrumentations and infrastructures, such as the UCLA Anatomic Pathology IHC Laboratory (CLIA approved lab).

Method:

- Bake slides for 1 hour at 65°C.

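### Section 11 defines TCR clonality as normalized Shannon entropy without the inversion in Section 18.1, so applied literally it reverses the sign of the clonality result

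*Combined protocol and SAP*

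**What the plan says.** Two parts of the document define the same metric.

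- **Section 11.1d (Cohort A):** "we will compute the clonality metric as the normalized Shannon entropy for all patients at baseline, Week 4, and resection". The paragraph opens with the hypothesis: "To assess the hypothesis that TCR clonality is higher in DM patients who respond". The change from baseline to resection is compared between responders and non-responders with a two-sample t-test at two-sided 0.05, and the comparison is repeated for the change to Week 4. The plan claims "80% power to detect a difference in clonality change of 1.35 standard deviations" with 25% responders.
- **Section 11.2d (Cohort B):** "we will compute the clonality metric as the normalized Shannon entropy for all patients at baseline, Week 4, and progression". The hypothesis and test are the same, with progression as the late time point. The plan claims "80% power to detect a difference in clonality change of 1.61 standard deviations" with 20% responders.
- **Section 18.1 (analysis of TCR clonality):** entropy is normalized by "dividing Shannon entropy by the logarithm of the number of unique productive TCR sequences in the data set", and one more step follows: "This normalized entropy value will be then inverted (12 normalized entropy) to produce our clonality metric". The stated purpose is to learn whether the T-cell response is "targeting specific tumor antigen (mono-clonal) or a non-specific process (poly-clonal) in the tumors".

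The clonality paragraphs in Section 11 neither mention an inversion nor refer to Section 18.1 for the formula.

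**The concern.** Un-inverted, normalized entropy is a diversity measure and moves opposite to clonality. Section 11 calls it the clonality metric and, in the same sentence, expects clonality to be higher in responders. Section 18.1 shares that expectation, since it links a mono-clonal repertoire to a specific anti-tumor response, but its formula agrees with it.

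Objective 1.3c is to correlate clonality with response, so the direction of the difference is the scientific answer. If the Section 11 wording is programmed as it stands, a finding that supports the hypothesis would be reported as contradicting it, and the reverse. The test would give no warning, because the two-sided p-value is the same under either coding.

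**Working it through.** **Inputs from the plan.** Cohort A: 25 patients, 25% responders, 1.35 SD. Cohort B: 21 patients, 20% responders, 1.61 SD. Both: two-sample t-test, two-sided alpha 0.05, stated power 80% (Sections 11.1 and 11.2).

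**Step 1: reproduce the stated power.** The noncentrality is d × √(n1·n2/(n1+n2)) with n1+n2−2 degrees of freedom, and power comes from the noncentral t distribution.

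- Cohort A, 6.25 vs 18.75: 1.35 × √4.6875 = 2.92 on 23 df; power 79.9%.
- Cohort B, 4.2 vs 16.8: 1.61 × √3.36 = 2.95 on 19 df; power 79.9%.
- Whole-number groups: 6 vs 19 gives 78.8%, and 4 vs 17 gives 78.5%.

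The plan's 80% is confirmed in both cohorts.

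**Step 2: direction of the metric.** Let h = H/log(N), where H is Shannon entropy and N the number of unique productive sequences. The repertoires below are illustrative, with the remaining clones equal in size.

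| Repertoire | h (Section 11) | 1 − h (Section 18.1) |
|---|---|---|
| N = 100, all equal | 1.00 | 0.00 |
| N = 100, one clone at 50% | 0.65 | 0.35 |
| N = 100, one clone at 90% | 0.17 | 0.83 |
| N = 1,000, one clone at 50% | 0.60 | 0.40 |

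For the second row, H = 0.5·ln 2 + 0.5·ln 198 = 2.99, and 2.99/ln 100 = 2.99/4.61 = 0.65. As one clone takes over, h falls and 1 − h rises.

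**Step 3: effect on the test.** The change in 1 − h is (1 − h_late) − (1 − h_base) = −(h_late − h_base). Every patient's change flips sign and the standard deviation stays the same. So t changes sign, while |t|, the two-sided p-value, power and detectable difference do not. In one simulated data set (assumed values, 6 vs 19 patients), h gave t = −2.88, p = 0.0084; 1 − h gave t = +2.88, p = 0.0084.

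**Step 4: size under the plan's own design differences.** Assume responders are truly higher in clonality change by 1.35 SD (A, 6 vs 19) or 1.61 SD (B, 4 vs 17). From 200,000 simulated trials per cohort:

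| Metric used | Significant in hypothesized direction, A / B | Significant in contrary direction, A / B |
|---|---|---|
| 1 − h (Section 18.1) | 79% / 78% | 0.001% or less in each |
| h (Section 11 as worded) | 0.001% or less in each | 79% / 78% |

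**Step 5: reach.** Four comparisons are affected: the late sample (resection in A, progression in B) and Week 4, in each cohort.

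**The case against.** The strongest reply is that this is a wording slip that Section 18.1 already covers. Section 11 cannot be run on its own, because it does not give the normalizer or say which sequences count. Anyone who looks these up finds them in the Section 18.1 paragraph that also inverts the value. Sections 15.1 and 18.2 send the reader to 18.1 for the translational work, and the hypothesis fits only the inverted form. The intended metric is therefore not in much doubt. But nothing gives 18.1 precedence, and Section 11 is the part a statistician programs from. A laboratory and an analyst who each follow their own section could end up with opposite signs.

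The objection also notes that no inference changes: the tests are two-sided, no decision rule uses clonality, and the objective is exploratory. This stands, and it limits the weight of the point.

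Lastly, the 79% and 78% show that the two codings are mirror images; they do not predict results. This also stands. The 1.35 and 1.61 SD are detectable differences, not expected effects. The figures assume paired samples from every patient, yet Section 15.1 makes the progression biopsy optional and requires the week 3 to 5 biopsy only where there is residual disease. The hypothesis is worded as a level while the test uses change, so taking responders as higher in change is a natural assumption that the plan does not state.

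**Conclusion.** The concern holds. Sections 11.1d and 11.2d define the clonality metric in the direction opposite to their own hypothesis and to Section 18.1. Followed literally, they reverse the sign in all four clonality comparisons. If the Section 18.1 metric is used, the direction is right and only the Section 11 wording is wrong; this is the likelier intent. The consequence is confined to the sign and interpretation of objective 1.3c. Type I error, two-sided p-values, power, detectable differences and the pCR and CR endpoints are untouched.

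One assumption matters: the 12 in the parenthesis of Section 18.1 is read as a damaged 1 minus. The conflict of direction does not depend on it, because the word for inversion is intact and a reciprocal would also fall as entropy rises. Only the exact equality of p-values depends on it.

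**What to change.** In Sections 11.1d and 11.2d, replace the normalized Shannon entropy with 1 minus the normalized Shannon entropy, as defined in Section 18.1. When doing so, confirm that the parenthesis in Section 18.1 does read as 1 minus, so that the formula is the same in all three places.

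The cost is one phrase in two places. Data collection, sample size, test and power do not change. Fixing the definition in writing also avoids any appearance that the sign convention was chosen after the results were seen.
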